4.2 Scientific Rationale of Trial Design

This study is designed as a standard double-blind placebo-controlled single administration, dose-ranging study to evaluate the effect of 2 different doses (high and medium dose) of VXA-GII.4-NS plus VXA-G1.1-NN in the target population, compared with placebo.

4.3 Justification for Dose Selection

Vaxart has previously completed dose escalation (Protocol VXA-G11-101) and dose optimization (Protocol VXA-G11-102) studies in its initial Phase 1 NoV vaccine studies to demonstrate the safety, tolerability, and immunogenicity of the VXA-G1.1-NN vaccine candidate. A Phase 1b, double-blind, placebo-controlled study (Protocol VXA-NVV-103) with VXA-G1.1-NN and VXA-GII.4-NS with monovalent or bivalent dosing have also been completed. Additionally, dose ranging studies from 1×10^8 IU – 1×10^{11} IU (2 doses) have been studied across multiple studies with the same vaccine platform.

Safety results from these completed oral tablet vaccine studies support investigations of bivalent administration of the VXA-G1.1-NN and VXA-GII.4-NS vaccine candidates at single total dose of 1×10^{11} IU per vaccine or 2×10^{11} IU per administration.

4.4 End of the Study Definition

A subject is considered to have completed the study if he/she completes the study active period at Day 29 (End of Study Active Period). Following completion of the Day 29 visit by all subjects the database will be cleaned and locked, and the study unblinded. The CSR will be written based on the Day 29 dataset.

A subject is considered to have completed the Safety Follow-up Period if he/she remains in the study Day 365 (Month 12). Following completion of the Day 365 tele-health appointment of all subjects, the safety database will be cleaned and locked, and data collected during the Follow-Up Period will be used to generate a CSR addendum.

4.5 Premature Termination or Suspension of Trial

The Sponsor or designee reserves the right to terminate the study at any time for any reason at the sole discretion of the Sponsor. This trial may be temporarily suspended, or prematurely terminated if there is sufficient reasonable cause. Written notification, documenting the reason for trial suspension or termination, will be provided by the suspending, or terminating party to study subjects, Investigators, funding agency, the Investigational New Drug (IND) Sponsor and regulatory authorities. If the study is prematurely terminated or suspended, the site Principal Investigator (PI) will promptly inform study subjects, the site Institutional Review Board (IRB) (if applicable) and will provide the reason(s) for the termination or suspension. Study subjects will be contacted, as applicable, and be informed of changes if any, to the study visit schedule.

Circumstances that may warrant termination or suspension include, but are not limited to:

- Determination of unexpected, significant, or unacceptable risk to subjects
- Insufficient compliance to protocol requirements
- Data that are not sufficiently complete and/or evaluable
- Determination that the primary endpoint has been met
- Determination of futility

Study may resume once concerns about safety, protocol compliance, and data quality are addressed, and satisfy the Sponsor, IRB/IEC, Food and Drug Administration (FDA) and/or South African Health Products Regulatory Authority.

4.6 Trial and Site Start and Close-Out

4.6.1 First Act of Recruitment

The study start date is the date on which the clinical study will be open for recruitment of subjects. The first act of recruitment is the first site open and will be the study start date.

4.6.2 Study/Site Termination

The Sponsor or designee reserves the right to close the study site at any time for any reason at the sole discretion of the Sponsor. Study sites will be closed upon study completion. A study site is considered closed when all required documents and study supplies have been collected and a study-site closure visit has been performed.

The Investigator may initiate study-site closure at any time, provided there is reasonable cause and sufficient notice is given to Sponsor and subjects in advance of the intended termination.

Reasons for the early closure of a study site by the Sponsor or Investigator may include but are not limited to:

- Failure of the Investigator to comply with the protocol, the requirements of the IRB/IEC or local health authorities, the Sponsor's procedures, or GCP guidelines.
- Inadequate or no recruitment (evaluated after a reasonable amount of time) of subjects by the Investigator.

- Total number of subjects included is achieved earlier than expected.

The Investigator shall promptly inform the subject and should assure appropriate subject therapy and/or follow-up.

5. SELECTION OF TRIAL POPULATION

5.1. Inclusion Criteria

To be eligible for this study, subjects must meet all the following:

Age

1. ≥ 18 years old at the time of signing the Informed Consent Form (ICF) and her infant will be aged >30 days to 11 months of age at the time of the participants' study drug administration

Type of Subjects

2. In stable and good general health, without significant medical illness, based on medical history, physical examination (including vital signs), and clinical judgment of the investigator.
3. Lactating females willing and able to provide informed consent which includes compliance with the requirements and restrictions listed in the ICF and in the protocol.
4. Lactating females who are willing to provide consent for their breastfed infant will be enrolled in the study
5. Negative pregnancy test prior to dose
6. Available for all planned visits and tele-health appointments, and ability to comply with all study-related evaluations (including ability and willingness to swallow multiple small enteric-coated tablets per study dose).
7. Plan to continue breastfeeding as the main source of the infant's nutrition for at least 1 month (longer is preferred with goal of 6 months post dose if possible) from the time of study drug administration. Exclusive breastfeeding is acceptable but not necessary.
8. The nursing infant is the product of a singleton pregnancy AND does not have any of the following (therefore, subjects must be willing to provide the infant's medical record at screening and Day 1 and the infant's updated vaccine record at Day 60 or later):
 - a. Any abnormality that may interfere with breastfeeding or milk absorption
 - b. Active infection (may be included if the infection resolves and the subject is re-assessed during the screening period)
 - c. Infant has any other medical condition or abnormality that, in the opinion of the investigator, could compromise the infant's appropriate inclusion in this study including interference with the interpretation of study results (such as malabsorption)
 - d. One or more documented brief resolved unexplained events (BRUE)

- e. Extreme prematurity (infants who were born at less than 28 weeks gestation)
 - f. 30 days of age or less at the participant's study drug administration OR greater than 11 months of age at the participant's study drug administration
 - g. Prior hospitalization that is not exclusively for hyperbilirubinemia requiring phototherapy
 - h. Any genetic/metabolic disease
 - i. Any chronic illness requiring long term medication
- 9. Subjects must be willing to use a highly effective form of contraception for 30 days prior to vaccination and until 60 days after the vaccination. Acceptable forms are oral, implantable, intrauterine, transdermal, intravaginal, injectable, double barrier or abstinence (subjects using diaphragms must also use condom). The form of contraception must be approved by the investigator.

Subject Exclusion Criteria:

The participants must be excluded from participating in the study if they meet any of the following:

1. Presence of a fever $\geq 38^{\circ}\text{C}$ measured orally at baseline, on Day 1 prior to vaccination. (Assessment may be repeated once during screening period)
2. Acute disease within 72 hours prior to vaccination is defined as the presence of a moderate or severe illness (as determined by the Investigator through medical history and physical exam). (Assessment may be repeated once during screening period.)
3. Who have received antipyretic/analgesic medications within 24 hours prior to the intended vaccine administration
4. Positive human immunodeficiency virus (HIV), Hepatitis B surface antigen (HBsAg), or hepatitis C virus (HCV) tests at the screening visit
5. History of hypersensitivity or allergic reaction to any component of the investigational vaccine, including but not limited to fish gelatin
6. History of serious reactions to vaccination such as anaphylaxis, respiratory problems, hives, or abdominal pain
7. Presence of significant uncontrolled medical or psychiatric illness (acute or chronic) including the institution of new medical/surgical treatment or significant dose alteration for uncontrolled symptoms or drug toxicity within 3 months of screening and reconfirmed at baseline
8. History of significant pregnancy-related complications during this pregnancy, including but not limited to pre-eclampsia, eclampsia, or gestational diabetes unless a full resolution is documented.
9. Cancer, or treatment for cancer, within the past 3 years (excluding fully treated and resolved basal cell carcinoma or squamous cell carcinoma)

10. Presence of immunosuppression or medical condition possibly associated with impaired immune responsiveness, including diabetes mellitus
11. History of irritable bowel disease or other inflammatory digestive or gastrointestinal condition that could affect the distribution/safety evaluation of an orally administered vaccine targeting the mucosa of the small intestine. Such conditions may include but are not limited to:
 - a. Any history of:
 - i. Malignancy
 - ii. Malabsorption
 - iii. Pancreatobiliary disorders
 - iv. Inflammatory bowel disease
 - v. Irritable bowel disease
 - vi. Hiatal hernia
 - vii. Surgical resection
 - b. History of diagnosis or treatment in past 5 years of:
 - v. Esophageal or gastric motility disorder
 - vi. GERD (Will allow for subjects with a history of pregnancy-related GERD if fully resolved for >3 months and no other history of GERD diagnosis)
 - vii. Peptic ulcer
 - viii. Cholecystectomy
12. Any condition that resulted in the absence or removal of the spleen
13. History of any form of angioedema
14. Diagnosed bleeding disorder or significant bruising or bleeding difficulties that could make blood draws problematic
15. History of GI bleeding including hematochezia (blood in stool) or melena (black stool)
16. Any significant hospitalization within the last year which in the opinion of the investigator or sponsor could interfere with study participation.
17. Any of the following history or conditions that may lead to a higher risk of clotting events and/or thrombocytopenia:
 - a. Family or personal history of bleeding or thrombosis
 - b. History of heparin-related thrombotic events, and/or receiving heparin treatments
 - c. History of autoimmune or inflammatory disease
 - d. Presence of any of the following conditions known to increase the risk of thrombosis within 6 months prior to screening:
 - i. Recent surgery other than fully healed cesarean delivery or excision/biopsy of cutaneous lesions
 - ii. Immobility (confined to bed or wheelchair for 3 or more successive days)
 - iii. Head trauma with loss of consciousness or documented brain injury
 - iv. Receipt of anticoagulants for prophylaxis of thrombosis
 - v. Recent clinically significant infection

18. Any other condition that in the clinical judgment of the investigator would jeopardize the safety or rights of a participant taking in the study, would render the participant unable to comply with the protocol, or would interfere with the evaluation of the study endpoints
19. Receipt of a licensed vaccine (including any COVID-19 vaccines under Emergency Use Authorization) within 14 days prior to study drug dose or planned administration during the study active period.
20. Use of antibiotics, proton pump inhibitors, H2 blockers, or antacids within 7 days prior to study drug administration or planned use during the active study period
21. Use of medications known to affect the immune function (including but not limited to systemic corticosteroids, leukotriene modifiers, and JAK inhibitors) within 2 weeks before study drug administration or planned use during the active study period. Ophthalmic, inhaled, and intranasal steroids should follow these restrictions.
22. Daily use of nonsteroidal anti-inflammatory drugs within 7 days prior to study drug administration or planned use during the active study period
23. Donation or receipt of blood or blood products within 30 days prior to study drug administration or planned donation during the active study period
24. Participants participating in any clinical trial with another investigational product 30 days prior to the first trial visit or intend to participate in another clinical trial at any time during the conduct of this trial
25. Are first-degree relatives of individuals involved in trial conduct.
26. Positive urine drug screen for drugs of abuse at screening
27. Positive alcohol test at screening or baseline
28. History of drug, alcohol, or chemical abuse within 1 year of screening

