3.2.2. Secondary End Points

- **Safety**

- Frequency, duration, and severity of all SAEs, AESIs, and NOCIs through 12 months after last study drug dose

- **Immunogenicity**

- Serum VP1 specific (GI.1 and GII.4) IgA through 6 months after study drug dose measured by Meso Scale Discovery (MSD) assay by dose level
 - Geometric mean concentration (GMC) at Day 180
 - Geometric mean fold rise (GMFR) from Day 1 to Day 180
- Breastmilk VP1 specific (GI.1 and GII.4) IgA through 6 months after study drug dose measured by Meso Scale Discovery (MSD) by dose level
 - Geometric mean concentration (GMC) at Day 60 and Day 180
 - Geometric mean fold rise (GMFR) from Day 1 to Day 60 and from Day 1 to Day 180
- Serum VP1 specific (GI.1 and GII.4) IgG through 6 months after study drug dose measured by Meso Scale Discovery (MSD) assay by dose level
 - Geometric mean concentration (GMC) at Day 1, Day 8, Day 29, and Day 180
 - Geometric mean fold rise (GMFR) from Day 1 to Day 8, from Day 1 to Day 29, and from Day 1 to Day 180
- Serum Blocking titers 50 (BT50) (GI.1 and GII.4) through 6 months after study drug dose measured by Histo-blood group antigen (HBGA) assay by dose level
 - Geometric mean titer (GMT) at Day 1, Day 8, Day 29, and Day 180
 - Geometric mean fold rise (GMFR) from Day 1 to Day 8, from Day 1 to Day 29, and from Day 1 to Day 180

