7.1.3. Procedure to be followed during follow-up period (Day 30 to Day 365)

- Verify understanding of and compliance with protocol requirements for contraception (see [Appendix 4](#)).
- Subjects will return to the site on Day 60 and Day 180:
 1. A blood sample will be collected for immunogenicity assessment on D180 as specified in the SoA ([Table 1](#)).
 2. Nasal and saliva samples will be collected for immunogenicity assessment on Day 60 and Day 180 as specified in the SoA ([Table 1](#)).
 3. Ascertain if the subject is still breastfeeding. If they are then ensure the subject has also collected breastmilk sample and infant stool sample during the timepoints specified in the SoA ([Table 1](#)), if not then remind the subject. Review with the subject how the collection was done and if the samples were properly stored.
 4. Collect the most current infant vaccine record on Day 60 or any time after.
- Collect and record SAEs, AESIs and NOCIs.
- Complete the source documents.
- The Investigator or an authorized designee completes the eCRFs.
- Ask the subject to contact the site staff or Investigator if an adverse event (e.g., doctor's visit, emergency room visit) or hospitalization occurs.
- The subjects will be contacted by phone between site visits on Day 120, Day 240, Day 300, and Day 365 to monitor for safety as specified in the SoA ([Table 1](#)). If the study personnel are unable to contact the subject with 3 attempts, the study personnel will follow instructions given in [Section 5.4](#).

7.1.4 Follow-up of Subjects with Related AEs or with AEs that Led to Study Discontinuation

Unless the subject refuses further contact, each subject who experiences an AE (whether serious or non-serious) during the study must be followed until the condition resolves, becomes stable, or

becomes chronic (even after the end of the subject's participation in the study) if either of the following is true.

- The AE is considered by the Investigator to be related to the product administered.
- The AE caused the discontinuation of the subject from the study.

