### 2.2.2 Secondary objective(s)

- **Safety**
  - To determine the long-term safety of bivalent GI.1/GII.4 norovirus vaccine through 12 months after the last vaccination.
- **Immunogenicity**
  - To assess the long-term immunogenicity of oral bivalent GI.1/GII.4 norovirus vaccine administration in healthy lactating female participants and most critically, the association with vaccine specific antibody responses in breast milk.

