#### For Immunogenicity quantitative data:

Immunological parameters below the Lower Limit Of Quantification (LLOQ) or the Limit Of Detection (LOD) (when available) will be imputed by half the lower limit of quantification or half the limit of detection for the descriptive summary. Immunological parameters above the Upper Limit of Quantification (ULOQ) will be imputed by multiplying by 2.

Such substitutions will be clearly documented in the footnotes of relevant outputs.

Missing immunogenicity results will not be replaced nor extrapolated.

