**20. FIGURES**

Figure Number	Figure Title	Population
14.2	Immunogenicity	
14.2.1.1	Serum VP1 specific GI.1 IgA Geometric Mean Concentration Bar Plot Over Time by Treatment Arm, between Day 1 to Day 29	Immunogenicity
14.2.1.2	Serum VP1 specific GI.1 IgA Geometric Mean Concentration Bar Plot Over Time by Treatment Arm, between Day 1 to Day 180	Immunogenicity
14.2.2.1	Serum VP1 specific GII.4 IgA Geometric Mean Concentration Bar Plot, by Treatment Arm, between Day 1 to Day 29	Immunogenicity
14.2.2.2	Serum VP1 specific GII.4 IgA Geometric Mean Concentration Bar Plot, by Treatment Arm, between Day 1 to Day 180	Immunogenicity
14.2.3.1	Breast Milk VP1 specific GI.1 IgA Geometric Mean Concentration Bar Plot Over Time by Treatment Arm, between Day 1 to Day 29	Immunogenicity
14.2.3.2	Breast Milk VP1 specific GI.1 IgA Geometric Mean Concentration Bar Plot Over Time by Treatment Arm, between Day 1 to Day 180	Immunogenicity
14.2.4.1	Breast Milk VPI specific GII.4 IgA Geometric Mean Concentration Bar Plot, by Treatment Arm, between Day 1 to Day 29	Immunogenicity
14.2.4.2	Breast Milk VPI specific GII.4 IgA Geometric Mean Concentration Bar Plot, by Treatment Arm, between Day 1 to Day 180	Immunogenicity
14.2.5.1	Serum VP1 specific GI.1 IgG Geometric Mean Concentration Bar Plot, by Treatment Arm, between Day 1 to Day 29	Immunogenicity
14.2.5.2	Serum VP1 specific GI.1 IgG Geometric Mean Concentration Bar Plot, by Treatment Arm, between Day 1 to Day 180	Immunogenicity
14.2.6.1	Serum VP1 specific GII.4 IgG Geometric Mean Concentration Bar Plot, by Treatment Arm, between Day 1 to Day 29	Immunogenicity
14.2.6.2	Serum VP1 specific GII.4 IgG Geometric Mean Concentration Bar Plot, by Treatment Arm, between Day 1 to Day 180	Immunogenicity
14.2.7.1	Serum Blocking Titers 50 (BT50) GI.1 IgG Geometric Mean Titer Bar Plot, by Treatment Arm, between Day 1 to Day 29	Immunogenicity
14.2.8.1	Serum Blocking Titers 50 (BT50) GII.4 IgG Geometric Mean Titer Bar Plot Over Time by Treatment Arm, between Day 1 to Day 29	Immunogenicity

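### Day 60 and Day 180 milk comes only from women still breastfeeding, so milk GMCs over time, and Day 29 against Day 180 fold rises, rest on different subsets of women: add a same-women display

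*Protocol*

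**What the plan says.** All protocol references are to version 2.0.

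- **Eligibility.** Protocol 5.1, criterion 7, requires a woman to "Plan to continue breastfeeding as the main source of the infant's nutrition for at least 1 month". The same criterion adds that "longer is preferred with goal of 6 months post dose if possible". Criterion 1 says that "her infant will be aged >30 days to 11 months of age at the time of the participants' study drug administration".
- **Late collection.** For the Day 60 and Day 180 visits, Protocol 7.1.3 tells the site: "Ascertain if the subject is still breastfeeding. If they are then ensure the subject has also collected breastmilk sample and infant stool sample".
- **Endpoints.** Protocol 3.2.2 and SAP 2.3.2 make milk IgA a secondary endpoint as "Geometric mean concentration (GMC) at Day 60 and Day 180", with the fold rise (GMFR) from Day 1 to each of those days. The SAP 2.2.2 objective they serve is "To assess the long-term immunogenicity of oral bivalent GI.1/GII.4 norovirus vaccine administration", with the milk response singled out as the most critical part.
- **Missing data.** SAP 3.5: "Missing immunogenicity results will not be replaced nor extrapolated".
- **Who is counted.** SAP 4.1.5 admits a dosed woman with one valid post-Day 1 result of any kind. SAP 14 averages log10 values over subjects in the arm and defines no cohort common to the visits. It computes fold rise per woman against her own Day 1 value.
- **Display.** SAP 20 plans a "Breast Milk VP1 specific GI.1 IgA Geometric Mean Concentration Bar Plot Over Time by Treatment Arm, between Day 1 to Day 180" (Figure 14.2.3.2) and a matching GII.4 plot (14.2.4.2). SAP 14 describes these bar charts for the two active arms.

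**The concern.** The planned milk displays will be read as a time course. The Day 1 and Day 29 values come from nearly the whole arm if women keep to the one-month plan. The Day 180 value comes from whoever still gives milk. If women who continue differ from those who stop in IgA level or in vaccine response, the bars can rise, hold or fall between visits although no woman's level has changed.

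The reporting order makes this more likely. SAP 16 puts the Day 29 results in the principal report and the later ones in an addendum, so a near-complete Day 29 figure will be set against a continuers-only Day 180 figure.

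What is at stake is the durability statement for milk IgA. The study is descriptive and tests no hypothesis, so these displays are its evidence on that question.

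The SAP offers little to detect the problem. It plans no summary of breastfeeding status and no analysis of women followed throughout. SAP 7.1 summarises only maternal characteristics; infant characteristics appear only in Listing 16.2.4.1.a. The one repeat analysis, on the per-protocol set when set sizes differ by more than 20%, uses a set that is not defined by milk availability.

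**Working it through.** The plan states no retention rate, SD or power for milk IgA, so there is no figure of its own to reproduce. What the documents fix is the structure: 30, 30 and 16 women per arm, a one-month breastfeeding plan, and an infant age at dosing of up to 11 months, hence at most 11 + 180/30.44 = 16.9 months at Day 180. Every other value below is an assumption.

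**1. Shift in GMC from composition alone.** Let p be the share of women still giving milk, SD the log10 SD of milk IgA, and r the correlation between log10 IgA and an underlying normal tendency to stay in lactation. Let z be the normal cut-point that retains p, and φ the normal density. The retained women's mean differs from the whole arm's by r × SD × φ(z)/p on the log10 scale, so the fold shift is 10^(r × SD × φ(z)/p). With r from 0.2 to 0.5 and SD from 0.3 to 0.5, r × SD runs from 0.06 to 0.25.

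| p | φ(z)/p | Fold shift, low to high |
|---|---|---|
| 80% | 0.350 | 1.05 to 1.22 |
| 60% | 0.644 | 1.09 to 1.45 |
| 40% | 0.966 | 1.14 to 1.74 |

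If r is negative the shift is the reciprocal, so the GMC falls.

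**2. Second route.** Suppose no woman changes and continuers have R times the GMC of stoppers. With a share f continuing, the plotted Day 180/Day 1 GMC ratio is R^(1−f).

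| R | f = 90% | 70% | 50% | 30% |
|---|---|---|---|---|
| 1.5 | 1.04 | 1.13 | 1.22 | 1.33 |
| 2 | 1.07 | 1.23 | 1.41 | 1.62 |
| 3 | 1.12 | 1.39 | 1.73 | 2.16 |

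**3. Is the fold rise from Day 1 affected?** A simulation of 30 women with no true change (20,000 repeats) gave available-case GMC ratios of 1.23 (f = 70%, R = 2), 1.42 (50%, 2) and 1.73 (50%, 3). The paired GMFR in the same runs was 0.999 to 1.001. Within one visit, pairing removes the problem.

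**4. Fold rises read across visits.** Let continuers have a stable 3-fold rise and stoppers a stable 2-fold rise. The Day 29 GMFR over all women is 3^f × 2^(1−f), which is 2.66 at f = 70% and 2.45 at f = 50%. The Day 180 GMFR, in continuers only, is 3.00. The apparent gain is 3.00/2.66 = 1.13 or 3.00/2.45 = 1.22, with no real change.

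**5. Precision with fewer women.** The 95% CI factor is 10^(t × SD/√n), with SD again 0.3 to 0.5. At n = 30 it is 1.29 to 1.54; at n = 15 (half of a vaccine arm), 1.47 to 1.89. For placebo it goes from 1.44 to 1.85 at n = 16 to 1.78 to 2.62 at n = 8.

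**The case against.** A reader might infer something stronger: that all the late milk results compare different women, so that the trial could report a durable or waning response that no woman showed. The documents do not support that.

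- The Day 60 and Day 180 GMFRs and the 2-, 3- and 4-fold rates set each woman against her own Day 1 value (SAP 14). Later women are a subset of the Day 1 women.
- Subject-level milk listings are planned (16.2.6.3 and 16.2.6.4), and SAP 3.1 reports the non-missing n, so some of the attrition will be visible.
- The primary Day 8 and Day 29 milk endpoints fall within the one-month plan.
- The 2-fold response threshold is no yardstick for the GMC shift. It applies to a within-woman ratio, which a change in composition does not distort.

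Four further points have weight. The protocol sets a six-month goal, and the synopsis version of criterion 6 expects women to be able to express milk. Criterion 7 concerns breastfeeding as main nutrition, whereas late collection needs only some breastfeeding, so the one-month floor says little about actual Day 180 loss. The milk tables use a signal per µg of total IgA, which may remove part of any lactation-stage effect. Placebo appears in the tables and would show a drift common to all arms, although from only 16 women at most.

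These points limit the likely size. They do not change the structure: a goal does not secure samples, normalisation does not alter who contributes, and the bar charts as described in SAP 14 leave placebo out. That the study is descriptive does not help either, since the display is then the result.

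**Conclusion.** The point holds for three things: the Day 60 and Day 180 milk GMCs, the Day 1 to Day 180 GMC plots, and any reading of GMFR or responder rates from Day 29 to Day 180. In each, a change over time can come from who is still lactating. It does not hold for a Day 60 or Day 180 GMFR or fold-rise rate taken alone. Those are internally sound and are limited only in that they describe women still giving milk.

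The size cannot be established from the documents. The range of about 1.05- to 1.74-fold, in either direction, rests wholly on assumed retention, SD and correlation, and its upper end needs the least favourable value of all three together. If nearly all women continue to Day 180, or if continuing is unrelated to IgA, the effect is negligible. This is a cheap improvement to a secondary analysis and does not threaten the primary endpoints.

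**What to change.** In SAP 14, Tables 14.2.2.3 and 14.2.2.4 and Figures 14.2.3.2 and 14.2.4.2, keep the all-available results and add beside them:

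1. Milk GMC and GMFR at Day 1, Day 29 and Day 60 (or Day 180) in women with a result at every visit shown.
2. The geometric mean within-woman Day 180/Day 29 ratio, with 95% CI, by arm.
3. The number of women with milk by arm and visit, placebo included, printed under each bar. Add breastfeeding status if the eCRF captures it. Sites ask about it, but no row of the Schedule of Activities and no planned output shows that it is recorded, so the display should rest on sample availability.
4. Infant age at dosing for women with and without Day 180 milk.

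Word the Day 60 and Day 180 conclusions as applying to women still lactating. The same-women display removes the change in composition between visits but still describes continuers only.

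The cost is SAP and table-shell wording, one added ratio, and fewer women with wider intervals in the same-women display (step 5 above). Eligibility, visits and clinical conduct stay as they are.
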